20.2 Completion of Electronic Case Report Forms

An eCRF will be used in this clinical trial. Staff authorized to enter or modify data on the eCRF will be assigned an appropriate user role:

- study coordinators or nurses may enter, modify, or delete data and may enter, modify, or delete responses to queries;
- investigators may perform the same activities as study coordinators. Moreover, they may authorize data by entering an electronic signature.

Any data entries, modifications, and deletions will be recorded in an automated audit trail together with a time stamp and the identification code of the person performing the entry / modification / deletion.

To access the eCRF authorized users will receive a unique user name and password that will also be required for data authorization (investigators only). These credentials are strictly personal and confidential and must not be shared with anyone.

Investigators will be provided with detailed eCRF Completion Guidelines that will identify the required data points to be collected, how to document them and when these data should be documented. Appropriate training in electronic data capture and support will be provided.

It is the responsibility of the Investigator to maintain adequate and accurate eCRFs to record (according to the eCRF Completion Guidelines) all observations and other data pertinent to the clinical trial obtained during scheduled or unscheduled visits. All eCRFs should be fully completed to ensure accurate data interpretation.

All eCRF entries should be made within a maximum of 5 days of a visit by a designated and trained member of the site staff. The Investigator must ensure the accuracy, completeness legibility and timeliness of data reported in the eCRF and all required reports. Any change or correction to an eCRF must be documented as instructed and explained (if necessary) in the clinic notes, this applies to both written and electronic changes. The patient's medical source documents must support any changes made.

Data reported in the eCRF that are derived from source documents should be consistent with the source documents or the discrepancies should be explained.

The investigator must review and electronically sign the completed eCRF casebook to verify its accuracy.

The main objective is to obtain those data required by the protocol in a complete, accurate, legible, and timely fashion. These data in the eCRF should be consistent with the relevant source documents.

The eCRFs and the corresponding electronic database shall be processed, evaluated, and stored in anonymous form in accordance with the data-protection regulations.

These data recorded in the course of this clinical trial may periodically be remotely reviewed and compared to the electronic database. The computerized handling of these data after receipt of the eCRFs may generate additional requests via electronic queries to which the Investigator is obliged to respond by confirming or modifying these data questioned. These requests with their responses will be appended to the eCRFs held by the Investigator and Sponsor.

In the case of missing data/remarks, the entry spaces provided for in the eCRF should be cancelled out to avoid unnecessary follow-up inquiries. The eCRFs are regulatory documents and must be suitable for electronic submission to authorities.

The Investigator must keep a separate patient identification list showing code numbers, names, and dates of birth to allow unambiguous identification of each patient included in the clinical trial. A note will be made in the hospital medical records that the patient is participating in a clinical trial. The eCRF will be completed appropriately.

20.3 Source Data and Patient Files

The Investigator has to keep a paper or electronic patient file for every patient participating in the clinical trial. In this patient file, the available demographic and medical information of a patient has to be documented, in particular the following: name, date of birth, sex, height, weight, patient history, concomitant diseases and concomitant medication (including changes during the clinical trial), statement of entry into the clinical trial, trial identification, patient number, the date of informed consent, all visit dates, pre-defined performed examinations and clinical findings, observed AEs (if applicable) and reason for withdrawal from clinical trial treatment or from the trial (if applicable). It should be possible to verify the inclusion and exclusion criteria for the clinical trial from the available data in this file. It must be possible to identify each patient by using this patient file.

Additionally, any other documents with source data, especially original printouts of data that were generated by technical equipment have to be filed. This may include laboratory value listings, electrocardiogram recordings, X-rays, computed tomography scans, etc. (if applicable). All these

documents have to bear at least the patient identification and the printing date printed by the recording device to indicate to which patient and to which procedure the document belongs. The medical evaluation of such records should be documented as necessary and signed/dated by the Investigator.

Printouts of computerized patient files must be signed and dated by the Investigator, and kept as a source document.

20.4 Investigator File and Archiving

The Sponsor will provide, and the investigator will maintain an Investigator Site File (ISF) containing all essential documents for the clinical trial. The ISF will contain each patient's eCRF pdf after the database has been locked. The investigator should maintain a record of the location(s) of their respective essential documents including source documents. The storage system used during the trial and for archiving (irrespective of the type of media used) should provide for document identification, version history, search and retrieval.

Essential documents are subject to audit and inspection at all times and will be archived according to applicable regulatory requirements.

20.5 Monitoring, Quality Assurance, and Inspection by Authorities

This clinical trial is to be conducted in accordance with ICH E6 (R2) and applicable European regulations. Monitoring and auditing of the trial will be the responsibility of the Sponsor or a designee authorized by the Sponsor.

To ensure compliance with ICH GCP guidelines and all applicable regulatory requirements, the Sponsor or its designee may conduct quality assurance audits. Regulatory agencies may also conduct a regulatory inspection of this clinical trial. Such audits or inspections can occur at any time during or after completion of the clinical trial. If audits or inspections occur, the Investigator and the institution agree to allow the auditor/inspector direct access to all relevant documents and to allocate his/her time and the time of his/her staff to the auditor/inspector to discuss findings and any relevant issues.

20.6 Data Management and Data Control

The Sponsor will be responsible for the processing and quality control of the data. Data management and filing will be carried out as described in the contracted CRO's Standard Operating Procedures for clinical trials.

Prior and concurrent medications within 30 days of randomization will be listed. Prior/concurrent medications will be coded using the World Health Organization Drug Dictionary classification

system and grouped by drug class and preferred term. AEs and current medical conditions for concomitant medications will be coded using MedDRA.

The eCRF data and patient data listings will be archived by the Sponsor for the lifetime of the product. No clinical trial document should be destroyed without prior written agreement between the Sponsor and the Investigator. Should the Investigator wish to assign the clinical trial records to another party or move them to another location, advance written notice should be given to the Sponsor.

21 FINANCING AND INSURANCE

A separate financial agreement (Clinical Investigators' Agreement) will be made between each Investigator and the Sponsor before the IMP is delivered. The Sponsor will ensure financing of the complete clinical trial.

The clinical trial is covered under a Sponsor group combined liability insurance policy. The certificate of insurance and an information leaflet containing essential information about the insurance coverage will be provided upon request.

22 PUBLICATIONS

After conclusion of the clinical trial, an integrated clinical and statistical study report will be prepared by the Sponsor or designee. The first publication of the clinical trial will comprise of data from the entire clinical trial population enrolled at all sites. Any publications of the results, either in part or in total (abstracts in journals or newspapers, oral presentations, etc.) by Investigators or their representatives will require pre-submission review by the Sponsor. The Sponsor is entitled to delay publication in order to obtain patent protection. For more details regarding publications, refer to the clinical trial agreement/Investigator trial agreement.

The results of the clinical trial will be published and/or presented in scientific meetings in a timely manner. Any formal publication of clinical trial results will be a collaborative effort between the Sponsor and the Investigator(s). All manuscripts and abstracts will be reviewed and approved in writing by the Sponsor prior to submission.

Policies regarding the publication of the clinical trial results are defined in the Clinical Investigator's Agreement.

25 APPENDIX II – ACCEPTABLE METHODS OF CONTRACEPTION

A woman is considered of childbearing potential, i.e. fertile, following menarche and until becoming post-menopausal unless permanently sterile. The status of post-menopausal is defined as no menses for 12 months without an alternative medical cause and/or the age of 60 years.

According to the Clinical Trial Facilitation Group (CTFG) dated 21/Sep/2020, the following methods are allowed for contraception during the clinical trial with a failure rate of less than 1%:

- combined (estrogen and progestogen containing) hormonal contraception associated with inhibition of ovulation ¹:
 - oral
 - intravaginal
 - transdermal
- progestogen-only hormonal contraception associated with inhibition of ovulation ¹:
 - oral
 - injectable
 - implantable ²
- intrauterine device (IUD) ²
- intrauterine hormone-releasing system (IUS) ²
- bilateral tubal occlusion ²
- vasectomised partner ^{2,3}
- sexual abstinence ⁴

From results of previous clinical trials with aerosolized L-CsA potential interactions between the IMP and hormonal contraceptives have not been investigated. It is recognized that hormonal contraceptives can increase serum levels of systemically dosed cyclosporine, but cyclosporine does not alter the efficacy of hormonal contraceptives. Subjects in the trial will be monitored for systemic cyclosporine levels.

¹ Hormonal contraception may be susceptible to interaction with the IMP, which may reduce the efficacy of the contraception method

² Contraception methods that in the context of this guidance are considered to have low user dependency.

³ Vasectomised partner is a highly effective birth control method provided that partner is the sole sexual partner of the WOCBP trial participant and that the vasectomised partner has received medical assessment of the surgical success.

⁴ In the context of this guidance sexual abstinence is considered a highly effective method only if defined as refraining from heterosexual intercourse during the entire period of risk associated with the study treatments. The reliability of sexual abstinence needs to be evaluated in relation to the duration of the clinical trial and the preferred and usual lifestyle of the subject.

### 3 ABBREVIATIONS

AE	Adverse Event
allo-HSCT	Allogeneic Hematopoietic Stem Cell Transplantation
ATC	Anatomical Therapeutic Chemical Classification System
AUC 0-4h	Area Under the Curve, 0 – 4 hours after dosing
BDRM	Blind Data Review Meeting
bid	Bis in die, twice daily
BOS	Bronchiolitis Obliterans Syndrome
CGI	Clinical Global Impressions
cGvHD	Chronic Graft Versus Host Disease
C max	Maximum Plasma Concentration
CsA	Cyclosporin A
CSR	Clinical Study Report
DMC	Data Monitoring Committee
eCRF	Electronic Case Report Form
EoS	End of Study
EoT	End of Treatment
FAS	Full Analysis Set
FEF 25-75	Forced Midexpiratory Flow
FEV 1	Forced Expiratory Volume in One Second
FVC	Forced Vital Capacity
IMP	Investigational Medicinal Product (study drug: L-CsA)
IPD	Important Protocol Deviation
L-CsA	Liposomal Cyclosporine A Inhalation Solution
MedDRA	Medical Dictionary for Regulatory Activities
MMRM	Mixed Model of Repeated Measures
N-IPD	Non-Important Protocol Deviation
PD	Protocol Deviation
PK	Pharmacokinetics
PPS	Per Protocol Set
PT	Preferred Term
Q1	1st quartile
Q3	3rd quartile
SAE	Serious Adverse Event
SAF	Safety Analysis Set

---

SAP	Statistical Analysis Plan
SAS	Statistical Analysis Software
SCT	Stem Cell Transplantation
SF-36	Short Form (36) Health Survey
SoC	Standard of Care
SOC	System Organ Class
TEAE	Treatment-Emergent Adverse Event
TFLs	Tables, figures and listings
$t_{max}$	Time Between Dosing and Maximum Plasma Concentration
WHO	World Health Organization

#### 4 VERSION HISTORY

Date	Version	Brief Description of Changes
25 FEB 2022	Final v1	No previous final version

## 5 INTRODUCTION

This Statistical Analysis Plan (SAP) provides details of planned analyses to be performed on the data to be collected from clinical trial BT – L-CsA – 201 – SCT (BOSTON-4). It is based on the Clinical Trial Protocol, version 5.0 of 30 April 2021 (including Protocol Amendment 4).

Modifications to this SAP will be subject to detailed documentation relating to timing and rationale, with a focus on identifying and providing a rationale for changes. Any deviations from the SAP will be fully described in the integrated clinical study report (CSR).

This SAP is not intended to pre-specify all possible analyses that may be performed after completion of the clinical trial. The main purpose of this SAP is to pre-specify statistical analyses that relate to identified clinical trial objectives. Any supportive or exploratory analyses presented in the integrated CSR which are not described in the SAP will be identified as such.

This SAP will be finalized before database lock or any unblinding for this study. The programming specifications including tables, figures and listings (TFLs) to support the analysis as described below will be presented as a separate document.

## 6 CHANGES TO STUDY PROTOCOL

The planned analysis will be performed according to the study protocol, its amendments and this statistical analysis plan. If there are contradictions between the study protocol or its amendments and this statistical analysis plan, the analysis will be performed according to this analysis plan. Any deviation from the planned analysis has to be described in the CSR.

The differences between study protocol and statistical analysis plan are summarized in the following table:

Change	Clinical Study Protocol (CSP)	In the Statistical Analysis Plan Will be changed to:
Wording in CSP	Major Protocol Deviation Minor Protocol Deviation	Important Protocol Deviation Non-Important Protocol Deviation

## 7 TRIAL OBJECTIVES

The primary objective of this study is to assess the tolerability and safety of two dose levels of aerosolized, liposomal cyclosporine A (L-CsA) in comparison to placebo, applied in addition to standard of care (SoC) therapy, for Bronchiolitis Obliterans Syndrome (BOS) in adult allogeneic hematopoietic stem cell transplantation (allo-HSCT) recipients. The secondary objectives are to assess the pharmacokinetics (PK) and exploratory efficacy and quality of life ratings of two dose

levels of aerosolized L-CsA in comparison to placebo in addition to SoC therapy in the same indication and patient population.

## 8 INVESTIGATIONAL PLAN

### 8.1 Trial Design

This is a Phase IIa, prospective, multicenter, randomized, single-blind, placebo-controlled clinical trial of L-CsA for the treatment of BOS in adults with confirmed BOS following allo-HSCT. Patients will receive either L-CsA 5 mg or L-CsA 10 mg or placebo via the **CCI** [REDACTED] System twice daily in addition to SoC treatment, for a period of 12 weeks (see Table 1).

A total of the following visits will be performed during the clinical trial:

- Screening
- Week 0 (Randomization/Baseline) [Visit 1]
- Week 2 [Visit 2]
- Week 4 [Visit 3]
- Week 8 [Visit 4]
- Week 12 (End of Treatment (EoT) [Visit 5]
- Week 14 (End of Study (EoS) [Visit 6]

After informed consent has been obtained, a Screening Visit will be carried out in order to determine the eligibility for randomized treatment. At the Baseline Visit (V1, randomization visit), inclusion and exclusion criteria will be re-confirmed and baseline spirometry performed. During the 12-week treatment period, interim visits are scheduled at weeks 2, 4, and 8 (V2 – V4). Visit 5 (End of Treatment, EoT) is scheduled to occur 12 weeks after Visit 1. Visit 6 (End of Study, EoS) is a safety follow-up visit performed 2 weeks after Visit 5/EoT.

However, if one of the visits V3, V4 and V6 cannot be performed at site due to COVID-19, remote visits (e.g., by telephone) are possible. COVID-19 related Adverse Events will be reported as SAEs.

COVID-19 specific consideration: the patients will be supplied during V1 with the full amount of study medication needed, to cover the total treatment period of 12 weeks. Patient has to bring all study medication back to the site at EoT Visit V5 for Drug Accountability.

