4 PROTOCOL SYNOPSIS

Protocol Title:	BOSTON-4: A Phase IIa Multi-Center, Randomized, Single-Blind Safety and Tolerability Study of inhaled Liposomal Cyclosporine A in Bronchiolitis Obliterans Syndrome Following Allogeneic Hematopoietic Stem Cell Transplantation
Sponsor:	Zambon SpA [name], [name] Italy
Protocol Number:	BT – L-CsA – 201 – SCT (BOSTON-4)
EUDRACT Number:	2019-000718-13
IND Number:	78,854
Investigational Medicinal Product:	Liposomal Cyclosporine A (L-CsA) Inhalation Solution 10 mg twice daily (bid) or Liposomal Cyclosporine A L-CsA Inhalation Solution 5 mg twice daily (bid) or Liposomal Placebo (0 mg L-CsA) Inhalation Solution twice daily (bid)
Protocol Phase:	Phase IIa
Protocol Date:	Version 5.0; 30 April 2021
Protocol Amendment	4
Clinical Trial Centers/Countries:	Up to 20 centers in Europe.
Planned Clinical Trial Period:	Duration of therapy: 12 weeks Total clinical trial duration per patient: up to 18 weeks
Planned Number of Patients:	24 patients randomized Randomization: 1:1:1 Patients will receive investigational treatment or placebo via the L-CsA specific [REDACTED] Nebulizer System (L-CsA [REDACTED CCI]), in addition to standard of care (SoC) therapy.

	Treatment A: L-CsA 10 mg bid plus SoC (n=8) Treatment B: L-CsA 5 mg bid plus SoC (n=8) Treatment C: L-CsA 0 mg (placebo) bid plus SoC (n=8)
Objective:	The objectives of this study are to assess the tolerability, safety, pharmacokinetics (PK), exploratory efficacy and quality of life of two doses of aerosolized L-CsA vs placebo in addition to SoC therapy for the treatment of BOS in adult allogeneic hematopoietic stem cell transplantation (allo-HSCT) recipients.
Clinical Trial Design:	Phase IIa prospective, multi-center, single-blind, randomized clinical trial assessing two doses of inhaled L-CsA and placebo.

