8.5 Stopping Rules and Discontinuation Criteria

8.5.1 Patient Level

Regular termination of clinical trial participation:

The investigational treatment will be terminated after 12 weeks (End of Treatment [EoT]). The treatment period will be followed by a 2-week follow-up period (End of Study [EoS]). Any patients with ongoing AEs and SAEs will be followed-up until recovery or stabilization of the AE/SAE.

Premature termination of clinical trial participation:

- Patients may discontinue participation in the clinical trial at any time by revoking their informed consent.
- The Investigator may withdraw a patient at any time if it is in the best interest of the patient based upon clinical assessments.
- Patient is lost to follow-up
- Pregnancy (the patient will be followed via the sponsor's safety department)
- Termination of the clinical trial as a whole by Zambon SpA as defined in [section 8.5.3](#).

If the participant fails to return for clinical follow-up, the patient will be contacted by telephone or a letter will be sent requesting a clinic visit (EoS), and the reason for non-compliance will be documented. The final visit will encompass the assessments listed under EoS Visit (Visit 6; [Section 13.2.5](#)). Additionally, used and unused IMP and inhalation device will be retrieved, if applicable. Zambon SpA will be notified that the patient has terminated clinical trial participation.

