12.1.4 Serious Adverse Event (SAE) Reporting

Any SAE occurring

- between the first clinical trial procedure after obtaining informed consent and within 2 weeks after the completion of the EoT Visit, whether or not considered related to the clinical trial treatment assignment.
or
- at any time after completion of the last follow-up and coming to the attention of the Investigator, if it is judged as related to the patient's participation in the clinical trial

must be reported to the Sponsor's Drug Safety (CCl) IMMEDIATELY, but within 24 hours upon knowledge, as follows:

- Document the event in the eCRF within 24 hours of discovery
- Submit the SAE report by Fax or e-mail to a list of predefined recipients
- Follow-up the SAE until the outcome is determined, providing periodic updates in the eCRF
- Provide any additional information if requested

Contacts of the Sponsor's Drug Safety are as follows:

CCI [REDACTED] [REDACTED] [REDACTED] [REDACTED] Belgium	Fax: CCI [REDACTED] Phone: CCI [REDACTED] E-Mail: CCI [REDACTED]
--	---

12.1.4.1 Timelines for Suspected Unexpected Serious Adverse Reaction (SUSAR) reporting to Competent Authorities and ECs

All suspected unexpected serious adverse reactions (SUSARs) will be reported by the Sponsor to the Competent Authorities and to the ECs concerned as soon as possible, but within a maximum of 15 days (fatal or life-threatening SUSARs within a maximum of 7 days) of first knowledge.

Relevant follow-up information of fatal or life-threatening SUSARs will be communicated subsequently within an additional 8 days.

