12.1.4.5 Duration of Follow-up after Adverse Events

All AEs should be followed until they are resolved or until a stable clinical endpoint is reached. The occurrence of AEs and SAEs will be monitored until 2 weeks after the EoT visit.

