## **9.2 Sample Size Considerations**

This is a Phase IIa study in a rare indication, with very limited availability of eligible patients and a purely descriptive statistical concept. Accordingly, the sample size for the study was established based on considerations of feasibility rather than on power calculations.

A total of 24 patients (3 arms with 8 patients in each) are planned to be randomized.

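### Visit 6 follows the EoT visit by 2 weeks in the text but has its own week window in the schedules, so the last planned safety contact can fall before the 2-week AE/SAE period ends

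*SAP*

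**What the plan says.** Several places time the end of follow-up from the EoT visit or from the end of treatment:

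- SAP 8.1: "Visit 6 (End of Study, EoS) is a safety follow-up visit performed 2 weeks after Visit 5/EoT".
- Protocol 12.1.4.5: "The occurrence of AEs and SAEs will be monitored until 2 weeks after the EoT visit".
- Protocol 12.1.4 requires SAEs to be reported if they occur up to or "within 2 weeks after the completion of the EoT Visit, whether or not considered related to the clinical trial treatment assignment".
- Protocol 8.5.1 describes a 2-week follow-up after the treatment period. It refers to the end of treatment, not to the date of the EoT visit.

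The Schedules of Activities (Protocol 13 and SAP Table 1) give each visit its own window: Visit 5/EoT at W 12 ± 7 days and Visit 6/EoS at W 14 ± 3 days. Nothing in either document says that the Visit 6 window moves with the actual date of Visit 5.

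Three places bear on where the weeks are counted from. SAP 8.1 labels Visit 1 as Week 0 and states that "Visit 5 (End of Treatment, EoT) is scheduled to occur 12 weeks after Visit 1". SAP 10.4 counts visit days from the randomization visit. The Protocol synopsis gives "Total clinical trial duration per patient: up to 18 weeks".

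**The concern.** The nominal times agree, since Week 12 plus 2 weeks is Week 14. The conflict comes from the anchor and the windows. Visit 5 may move by a week either way, but the Visit 6 window does not visibly move with it. A site can therefore keep both visits in window, record no deviation, and still hold the last scheduled safety contact before the 2-week AE/SAE period is over.

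Visit 6 is the only planned visit after EoT. Under Protocol 13.2.5 it carries the physical examination, vital signs, laboratory tests, pregnancy test, concomitant medication and AE questioning. No scheduled contact follows it. Safety and tolerability are the primary objective, and Protocol 5.1.1 describes this as the first study of the product in this population. It is worth making sure that the planned contact covers the stated period.

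**Working it through.** **Inputs**

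| Input | Value | Source |
|---|---|---|
| Visit 5 window | 12 weeks ± 7 days | Protocol 13; SAP Table 1 |
| Visit 6 window | 14 weeks ± 3 days | Protocol 13; SAP Table 1 |
| AE/SAE period after EoT visit | 14 days | Protocol 12.1.4, 12.1.4.5 |
| Screening | up to 4 weeks | Protocol 13 |
| Total per patient | up to 18 weeks | Protocol synopsis |

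**The plan's own figures.** The nominal gap is 14 × 7 − 12 × 7 = 98 − 84 = 14 days, which reproduces the stated 2 weeks. The total is 4 + 14 = 18 weeks, which reproduces the synopsis.

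**Which anchor?** If Visit 6 were timed from a late Visit 5, the total would be 4 + 13 + 2 = 19 weeks before any tolerance. The 18-week figure therefore fits a count from baseline better. The support is not decisive: counted from baseline, the latest Visit 6 gives (28 + 101)/7 = 18.4 weeks, so 18 is a nominal figure.

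**Reading A: both windows counted from baseline**

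- Visit 5: 84 ± 7 = day 77 to 91.
- Visit 6: 98 ± 3 = day 95 to 101.
- Minimum gap: 95 − 91 = 4 days.
- Maximum gap: 101 − 77 = 24 days.

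| Visit 5 on day | Gap if Visit 6 on day 95 | on day 98 | on day 101 |
|---|---|---|---|
| 81 | 14 | 17 | 20 |
| 84 | 11 | 14 | 17 |
| 87 | 8 | 11 | 14 |
| 88 | 7 | 10 | 13 |
| 91 | 4 | 7 | 10 |

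From day 88 on, even the latest Visit 6 is short of 14 days (101 − 88 = 13). That is 4 of the 15 permitted Visit 5 days (88 to 91). At the other end, a Visit 5 on days 77 to 80 always leaves more than 14 days (95 − 80 = 15).

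Of the 15 × 7 = 105 in-window day pairs, 49 give less than 14 days, 7 give exactly 14, and 105 − 49 − 7 = 49 give more. These are counts of permitted combinations, not probabilities.

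**Reading B: Visit 6 at actual EoT + 14 ± 3 days**

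The gap is 14 − 3 = 11 to 14 + 3 = 17 days. The extremes disappear, but Visit 6 can still come up to 3 days before the period ends.

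Under either reading an in-window Visit 6 can precede the end of the 2-week period. Only the size of the shortfall differs: up to 14 − 4 = 10 days under A, and up to 3 days under B.

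**The case against.** The strongest reply is that the conflict is inferred. Neither table prints a baseline anchor, and SAP 8.1 expressly places Visit 6 after Visit 5, so ± 3 days can be read as tolerance on EoT + 2 weeks. That stands: the 4-to-24-day range is conditional on Reading A. It does not remove the point, because Reading B also allows a shortfall and the documents do not say which reading applies.

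Four stronger inferences are tempting, and the documents do not support them.

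- **That SAEs after an early Visit 6 go unreported.** The SAE duty in Protocol 12.1.4 runs to 2 weeks after the EoT visit, whenever Visit 6 takes place, and later for related events. Protocol 12.1.1 tells patients to report symptoms between visits at once, and unscheduled visits are allowed (13.2.6). What is lost is a planned, solicited contact.
- **That the visit gap is time off drug.** Treatment is capped at 12 weeks (Protocol 8.3.2.2). If the last dose is on about day 84, a Visit 6 on day 95 to 101 is 11 to 17 days later, whatever the date of Visit 5. Protocol 13.2.3 does list IMP administration among the procedures for Visits 2 to 5, so the documents leave the last-dose date open when Visit 5 is late. Even so, the visit gap cannot be presented as off-drug observation.
- **That the main results are affected.** The primary assessment stops at Visit 3 (SAP 13). The secondary assessment covers the treatment period (SAP 14.1), the shift tables use V3 and EoT (SAP 13.3.2), and incidence densities are per patient day. The windows are the same in all arms. A small exposure remains: SAP 10.2.1 takes all data to the end of participation and the TEAE definition in SAP 10.3.1 has no end date, although SAP 13.3.1 describes the all-TEAE summary as onset during randomized treatment.
- **That a 4-day gap is typical.** It is 1 of 105 permitted pairs (day 91 with day 95). The documents give no information on how visit dates will be distributed.

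**Conclusion.** The point holds as a conflict over the Visit 6 anchor and window that needs reconciling. The text times Visit 6 and the AE/SAE period from EoT, while the schedules give a separate Visit 6 window. If the weeks are counted from baseline, which is inferred from the numbering and the 18-week total, the in-window gap is 4 to 24 days, and any Visit 5 from day 88 on rules out a compliant Visit 6 at 14 days or more. If Visit 6 moves with EoT, the gap is 11 to 17 days.

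The consequence is limited to safety capture. The last scheduled laboratory, vital-sign, examination and AE-questioning contact can come up to 10 days (or up to 3 days on the second reading) before the stated period closes. The reporting duty is unaffected, and the effect on the primary and secondary analyses is small. The point concerns patients who complete treatment; the follow-up length for patients withdrawn from IMP (Protocol 9.3.4) is a separate matter.

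**What to change.** In both Schedules of Activities (Protocol 13 and SAP Table 1), time Visit 6 from the actual EoT visit with a window that does not open before day 14, for example EoT + 14 to + 17 days. State the same window in SAP 8.1. The last solicited contact then always covers the 2-week period in Protocol 12.1.4 and 12.1.4.5. A window of EoT + 14 ± 3 days would remove the extremes but still allow day 11.

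Update the total duration in the synopsis as well. With 28 days of screening, Visit 5 on day 91 and Visit 6 17 days later, the maximum is (28 + 91 + 17)/7 = 136/7 = 19.4 weeks.

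The cost is wording in two tables and two text passages; no visit or test is added. A patient with Visit 5 on day 91 would have Visit 6 on day 105 to 108. That is 7 to 10 days after the nominal day 98, or 4 to 7 days after the latest day now allowed (day 101, counting from baseline).
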